**Abstract**

The coronavirus disease 2019 (COVID-19) pandemic is a serious global health threat. Multiple antiviral or immunomodulatory therapies have failed to show any mortality benefit for patients with COVID-19. Dexamethasone was shown in a large clinical trial to improve mortality. However, it is unclear what dose of dexamethasone is most beneficial in hospitalized patients with COVID-19. We plan to conduct a randomized single center open label clinical trial to evaluate two different doses of dexamethasone (20mg vs. 6mg) on the health outcome for hospitalized patients with COVID-19. The intervention arm is dexamethasone 20mg daily for 5 days, followed by dexamethasone 10mg daily for 5 days. The comparator is dexamethasone 6mg daily for 10 days. Three hundred participants will be enrolled. The primary outcome is clinical improvement using World Health Organization ordinal scale at day 28 or live discharge, whichever comes first. Our hypothesis is that patients who are treated with dexamethasone 20mg daily are more likely to have clinical improvement compare to those who are treated with dexamethasone 6mg daily on day 28.

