**A. Specific Aims**

Studies showed dexamethasone has the mortality benefit and increases in the number of ventilator-free days for patients with COVID-19. However, there is no published trial to compare the health outcome for COVID-19 patients who are treated with different doses of dexamethasone. The primary aim of this study is to test the effectiveness of two difference dexamethasone dose to treat COVID-19. The hypothesis is that dexamethasone 20mg daily treatment is superior over dexamethasone 6mg daily in clinical improvement at day 28 using WHO ordinal scale for clinical improvement (1, 2)

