### **D. Research Design and Methods (What, When, How, Where)**

1. Identify sources of research material in the form of biospecimens, records and/or data from interaction with participants.  
The electronic medical records demographic and clinical data on participants

will be collected and analyzed.

2. Describe study design, including sequence and timing of study procedures. Distinguish research procedures from those that are routine care. Provide a flow diagram or timetable.

- It is a single center open label randomized clinical trial to investigate the different dose of dexamethasone on the health outcomes in hospitalized moderate or severe COVID patients.
- It is a superiority trial.
- This trial has two parallel groups. The participants will be randomly assigned in a 1:1 ratio to intervention group and control group.
- We anticipate that approximately 300 participants will be enrolled and complete the study (Each group will enroll 150 participants.) The study plan to start as soon as the OUHSC IRB approves it and the duration is 28 days.
- The COVID patients will be screened in the first 24 hours after investigators are contacted.
- Participants will be randomized to intervention arm or control arm after participants agree to be enrolled into the study and sign the informed consent.
- Except for the different doses of dexamethasone, participants will receive the routine medical care in OUMC.

3. Include the study duration and number of study visits required.

This study will last for 5 months. There is only one visit for patients who are in OUMC for more than 28 days after randomization. There are two visits for patients who are not in OUMC at day 28 after randomization, first visit is the same as prior mentioned first visit, the second visit is a phone visit. The first visit is for screening, informed consent. After the visit, participants will be randomized and receive dexamethasone 20mg daily vs. 6mg daily. Participants will receive other routine medical care in the hospital till discharge. Research staff will review the hospital medical records daily to monitor the clinical improvement and any adverse event. At day 28, if participants are not in OUMC, research team will contact participants to evaluate the WHO ordinal scale.

4. Describe blinding, including justification for blinding or not blinding the trial.

This is an open label trial. The study outcome is objective. Not blinding the trial does not affect the study outcome.

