#### **E. Chart Review**

1. List the data that will be used from the chart review. Alternatively, attach a separate data collection tool.

The chart review is prospective in nature. We will collect individuals' basic characteristic and clinical variables, including date of birth, race/ethnicity, gender, insurance type, residential zip code, smoking history, height, weight, history of COVID vaccination, previous history of COVID, dexamethasone adverse events such as hyperglycemia, infections etc, respiratory support including nasal cannula oxygen, high flow oxygen, Bipap, mechanic ventilation, length of ICU stay, length of hospital stay, discharge disposition, health status 28 days after first dose of study dexamethasone eg. supplemental oxygen, tracheostomy, chronic mechanic support, daily activity limitation. We will also examine comorbidities including obesity, diabetes,

hypertension, hyperlipidemia, acute kidney injury, chronic kidney disease, heart failure, arrhythmia, coronary artery disease, psychological disease etc.

2. Describe the databases that will be utilized, including specific sites from which you will collect data.

We will collect data from Meditech database in OUMC.

3. Describe the process for obtaining and recording the records and at what point (if at all) the data is de-identified.

The investigators conduct a review of records from their practice and collects medical records based on inclusion/exclusion criteria. Records will be de-identified during data analysis.

4. Explain how access to the data will be controlled and whether the access is logged.

The electronic images of signed consent forms will be stored in a secured server in OUHSC campus. This secured server will be created with OUHSC IT service help. Only study team members have the access to the secured server. The data abstracted from Meditech will be stored in REDCap. Only research team members have the access to REDCap.

5. What happens to the data at the end of the study?

The electronic data will be stored in the secured server and REDCap after the project closure for future research reference.

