**H. Inclusion / Exclusion Criteria**

1. List the criteria that will define who will be **included** in the study

Age  $\geq$  18 years old

PCR confirmed COVID-19 infection

Positive pressure ventilation (non-invasive or invasive) or high flow nasal cannula (HFNC) or need supplemental oxygen with oxygen mask or nasal cannula

2. List the criteria that will define who will be **excluded** in the study.

Underlying disease requiring chronic corticosteroids

Severe adverse events before admission, i.e. cardiac arrest;

Contraindication for corticosteroids;

Death is deemed to be imminent and inevitable during the next 24 hours

Recruited in other clinical intervention trial

Pregnancy

Patient on judicial protection

3. Provide early termination criteria.

The study will be terminated early if COVID pandemic ends or there is no new COVID admission to OUMC or the interim data analysis (6 weeks after study start date) shows worse primary outcome in intervention group.

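### The primary outcome is scored at live discharge when that precedes day 28, but the hypothesis is improvement at day 28, and no rule covers death or worsening in between

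*Combined protocol and SAP*

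**What the plan says.** - **Abstract, endpoint:** "The primary outcome is clinical improvement using World Health Organization ordinal scale at day 28 or live discharge, whichever comes first".
- **Abstract, hypothesis (next sentence):** the high-dose group is more likely to improve "compare to those who are treated with dexamethasone 6mg daily on day 28".
- **A. Specific Aims:** the high dose is expected to be "superior over dexamethasone 6mg daily in clinical improvement at day 28 using WHO ordinal scale".
- **D. Research Design and Methods, item 3:** "At day 28, if participants are not in OUMC, research team will contact participants to evaluate the WHO ordinal scale". This is a phone visit for "patients who are not in OUMC at day 28 after randomization". In hospital, "Research staff will review the hospital medical records daily to monitor the clinical improvement and any adverse event".
- **E. Chart Review:** collects "health status 28 days after first dose of study dexamethasone", so its day 28 runs from first dose, whereas section D counts from randomisation.
- **H. Inclusion / Exclusion Criteria:** the lowest qualifying level of support is "need supplemental oxygen with oxygen mask or nasal cannula", which is score 4 in Table 1.
- **M. Statistical Methods:** improvement is described as sustained and means a change of more than 2 points, with no time point or duration. The planning rate is the 67.2% of a cited trial's dexamethasone group discharged within 28 days. The analysis paragraph lists the ordinal scale and death among the outcomes without saying which ordinal score is analysed.

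No section says how death, readmission or worsening between discharge and day 28 is counted in the primary outcome.

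**The concern.** The endpoint and the hypothesis name different scoring times, and they part for exactly those participants who leave hospital alive before day 28. For them the endpoint rule fixes the score at discharge, and nothing later can change it. Someone who goes from score 6 to score 1 at discharge and dies on day 20 is a success under the endpoint sentence and a failure under the hypothesis.

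Two statisticians following this plan could therefore report different primary results from the same data. The interim criterion in section H rests on the primary outcome too, so it inherits the ambiguity. This needs settling before outcome data are seen.

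**Working it through.** **1. Which participants can be misclassified.** Entry requires at least supplemental oxygen, so baseline is 4 to 7. Assume a live discharge scores 1 or 2. Improvement means baseline minus score > 2. A participant improved at discharge is no longer improved at day 28 if the score is then at least baseline − 2:

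| Baseline | Improved at discharge score | Reversed by day-28 score (> 2 rule) | Reversed by day-28 score (if read as ≥ 2) |
|---|---|---|---|
| 4 | 1 | 2 to 8 | 3 to 8 |
| 5 | 1 or 2 | 3 to 8 | 4 to 8 |
| 6 | 1 or 2 | 4 to 8 | 5 to 8 |
| 7 | 1 or 2 | 5 to 8 | 6 to 8 |

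(Under ≥ 2, a move from 4 to 2 also counts as improved.) Death, score 8, reverses improvement in every row under either reading. One opposite error exists under > 2 only: baseline 4, discharged at 2 (not improved), at 1 on day 28 (improved).

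**2. How many could be affected.** The documents give no post-discharge rate, so both inputs are assumptions: the share of 300 scored at discharge, and the fraction s of those who reverse. Bound = share × s, in percentage points (participants in brackets).

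| Share scored at discharge | s = 2% | s = 5% | s = 10% |
|---|---|---|---|
| 50% (150) | 1.0 (3) | 2.5 (7.5) | 5.0 (15) |
| 67.2% (about 202) | 1.3 (4) | 3.4 (10) | 6.7 (20) |
| 80% (240) | 1.6 (4.8) | 4.0 (12) | 8.0 (24) |

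These are upper bounds only for the assumed s, because not every discharged participant counts as improved. The 67.2% comes from a trial that also enrolled patients on no respiratory support.

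**3. The plan's own sample sizes.** Two-proportion formula, two-sided 0.05, 80% power, 1:1, with p̄ the mean of p1 and p2 and d their difference:

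n = [1.96·√(2p̄(1−p̄)) + 0.8416·√(p1(1−p1)+p2(1−p2))]² / d², then continuity-corrected n′ = (n/4)·[1+√(1+4/(nd))]².

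For 60% vs 75%, n = 151.9 and n′ = 164.9, so 165 per arm and 330 in total. All six rows of Table 2 reproduce: 330, 268, 176, 752, 626, 438. The arithmetic is not at issue.

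**4. Power for a day-28 endpoint.** Start from 67.2% vs 82.2% (the planning rate plus 15 points), with 150 per arm. Inverting the correction gives an effective n = 150·[1−1/(150d)]². Power = Φ{[d√n − 1.96·√(2p̄(1−p̄))] / √(p1(1−p1)+p2(1−p2))}. Assume a fraction f of improved participants reverses equally in both arms, so both rates are multiplied by 1 − f:

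| f (assumed) | Rates | Corrected power | Uncorrected power |
|---|---|---|---|
| 0 | 67.2% vs 82.2% | 81.8% | 85.2% |
| 5% | 63.8% vs 78.1% | 73.9% | 77.9% |
| 10% | 60.5% vs 74.0% | 66.0% | 70.4% |

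The upward 4-to-2-to-1 cases are left out; they would raise the rates.

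**5. Unequal reversal.** With f = 5% in control and 10% in high dose, the day-28 difference is 0.822×0.90 − 0.672×0.95 = 10.1 points. With the fractions swapped it is 0.822×0.95 − 0.672×0.90 = 17.6 points. The discharge-scored endpoint shows 15 points in both cases. Nothing in the documents favours either.

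**The case against.** - **The body of the plan points to day 28.** Specific Aims, the day-28 contact, the day-28 health status and the description of improvement as sustained all fit that reading; the discharge rule stands in one Abstract sentence. This is fair, and it means the literal reading may not be what was intended. But that sentence is the one that explicitly defines the primary outcome, and nothing says the body overrides it.
- **Discharge is a coherent endpoint.** The planning rate is discharge-based and fits it better than day-28 status. This stands, so keeping the rule is a legitimate option if the hypothesis is reworded and post-discharge death is dealt with.
- **A reader might infer that the day-28 score is wasted altogether.** The documents do not support that. It is the primary score for those not discharged alive earlier, and the Statistical Methods exclude no other use of it.
- **A reader might infer that deaths after discharge vanish from the trial.** They need not. Death is a separate outcome in section M, and the board reviews deaths under section N. Neither gives a time window, and neither corrects the primary score.
- **The illustrations mix unlike events.** Under the > 2 rule, a move from 1 to 2 after baseline 4 is a reversal, although it is only a reported activity limitation. Discharge disposition, tracheostomy and chronic ventilatory support are also collected, so some live discharges, for example to another facility, may not score 1 or 2. Both points stand and limit what the figures can carry.

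**Conclusion.** The conflict is in the text and must be resolved. The primary outcome and the hypothesis use different scoring times for participants discharged alive before day 28, and on the literal rule an improved participant who then dies by day 28 is counted as a success. That conclusion needs no numerical assumption.

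The size does. Under assumed reversal of 2% to 10% among the 50% to 80% assumed to be scored at discharge, the bound runs from 1.0 to 8.0 percentage points, against a target difference of 15. These figures depend on the assumed rates and on live discharges scoring 1 or 2.

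A reader might go further and conclude that the comparison is biased towards one dose. The documents do not support that: they give no post-discharge rate in either arm, so neither the size nor the direction of any effect between arms is known. The case for the change rests on the unresolved definition of the primary outcome.

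**What to change.** **Preferred change**

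- **Abstract:** remove the live-discharge alternative. Define the primary outcome for all randomised participants as improvement from baseline to day 28 after randomisation, using the section M threshold. Take the score from the hospital record or the already planned day-28 contact. Score death by day 28 as 8, and a stay in any hospital as hospitalised.
- **Section M, analysis:** name this as the score analysed. Pre-state two sensitivity analyses for participants not reached: last known status, and not improved. Report live discharge as a secondary outcome.
- **Section M, sample size:** state that the 67.2% is discharge-based and re-justify it for a day-28 status.
- **Section E:** count day 28 from randomisation, as section D does.

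**If the discharge rule is kept deliberately:** reword the hypothesis in the Abstract and Specific Aims to match, count death by day 28 as not improved, and pre-state day-28 status as a supporting analysis.

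**Cost.** These are mainly text changes, because the contact is already planned. Some contacts will fail: if 10% of 150 to 240 discharged participants are not reached (assumption), 15 to 24 scores are missing, or 5% to 8% of 300. Both sensitivity analyses are needed, since last known status alone would largely restore the discharge score. The planning rate, and with it power, may fall as shown in the working. Open-label influence remains, because discharge decisions still move the scale and scores 1 and 2 rest on reported activity limitation.

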**A. Specific Aims**

Studies showed dexamethasone has the mortality benefit and increases in the number of ventilator-free days for patients with COVID-19. However, there is no published trial to compare the health outcome for COVID-19 patients who are treated with different doses of dexamethasone. The primary aim of this study is to test the effectiveness of two difference dexamethasone dose to treat COVID-19. The hypothesis is that dexamethasone 20mg daily treatment is superior over dexamethasone 6mg daily in clinical improvement at day 28 using WHO ordinal scale for clinical improvement (1, 2)

**B. Background and Significance**

As of December 2020, COVID-19 - caused by severe acute respiratory syndrome coronavirus 2 (SARS-CoV-2) - has infected more than 20 million people with more than 350,000 deaths in the United States. (3) Several pharmacologic therapies for use in patients with COVID-19 have been investigated in randomized trials. Most antiviral or immunomodulatory therapies investigated have failed to show any mortality benefit. Only dexamethasone showed to improve mortality in RECOVERY trial. (4) In this randomized, controlled, open-label trial, dexamethasone 6 mg once daily (intravenous or by mouth) for up to 10 days reduced 28-day mortality in hospitalized patients with COVID-19. Another multicenter trial (CoDEX) using dexamethasone 20mg daily for 5 days, followed

by 10mg daily for 5 days revealed dexamethasone increase in the number of ventilator-free days.(5) However, there is no published trial to evaluate the difference of health outcomes using different dose of dexamethasone. Currently OUHSC COVID-19 Task Force recommends dexamethasone 6mg daily for 10 days for all hospitalized COVID-19 patients regardless of the respiratory status. (6) However, the COVID-19 morbidity and mortality remain high despite the recommended therapy. We plan to conduct a single center open label randomized clinical trial to investigate the health outcomes in hospitalized patients with COVID-19 treated with dexamethasone 20mg daily for 5 days, 10mg daily for 5 days (high dose) vs. dexamethasone 6mg daily for 10 days (low dose).

### **C. Preliminary Studies/Progress Report**

In RECOVERY trial, 2104 patients were assigned to receive dexamethasone 6mg daily for 10 days and 4321 to receive usual care (no dexamethasone). (4) Overall, 482 patients (22.9%) in the dexamethasone group and 1110 patients (25.7%) in the usual care group died within 28 days after randomization (age-adjusted rate ratio, 0.83; 95% confidence interval [CI], 0.75 to 0.93;  $P<0.001$ ). In the dexamethasone group, the incidence of death was lower than that in the usual care group among patients receiving invasive mechanical ventilation (29.3% vs. 41.4%; rate ratio, 0.64; 95% CI, 0.51 to 0.81) and among those receiving oxygen without invasive mechanical ventilation (23.3% vs. 26.2%; rate ratio, 0.82; 95% CI, 0.72 to 0.94) but not among those who were receiving no respiratory support at randomization (17.8% vs. 14.0%; rate ratio, 1.19; 95% CI, 0.91 to 1.55). This trial concluded that in patients hospitalized with Covid-19, the use of dexamethasone resulted in lower 28-day mortality among those who were receiving either invasive mechanical ventilation or oxygen alone at randomization but not among those receiving no respiratory support.

In CoDex trial, 151 patients received 20mg of dexamethasone daily for 5 days, 10mg of dexamethasone daily for 5 days or until ICU discharge and standard care, 148 patients received standard care only.(5) Patients in the dexamethasone group had a mean 6.6 ventilator-free days (95% CI, 5.0-8.2) during the first 28 days vs 4.0 ventilator-free days (95% CI, 2.9-5.4) in the standard care group (difference, 2.26; 95% CI, 0.2-4.38;  $P = 0.04$ ). Thirty-three patients (21.9%) in the dexamethasone group vs 43 (29.1%) in the standard care group experienced secondary infections, 47 (31.1%) vs 42 (28.3%) needed insulin for glucose control, and 5 (3.3%) vs 9 (6.1%) experienced other serious adverse events. It was concluded that among patients with COVID-19 and moderate or severe ARDS, use of intravenous dexamethasone plus standard care compared with standard care alone resulted in a statistically significant increase in the number of ventilator-free days (days alive and free of mechanical ventilation) over 28 days.

[figure not shown]
### **D. Research Design and Methods (What, When, How, Where)**

1. Identify sources of research material in the form of biospecimens, records and/or data from interaction with participants.  
The electronic medical records demographic and clinical data on participants

will be collected and analyzed.

2. Describe study design, including sequence and timing of study procedures. Distinguish research procedures from those that are routine care. Provide a flow diagram or timetable.

- It is a single center open label randomized clinical trial to investigate the different dose of dexamethasone on the health outcomes in hospitalized moderate or severe COVID patients.
- It is a superiority trial.
- This trial has two parallel groups. The participants will be randomly assigned in a 1:1 ratio to intervention group and control group.
- We anticipate that approximately 300 participants will be enrolled and complete the study (Each group will enroll 150 participants.) The study plan to start as soon as the OUHSC IRB approves it and the duration is 28 days.
- The COVID patients will be screened in the first 24 hours after investigators are contacted.
- Participants will be randomized to intervention arm or control arm after participants agree to be enrolled into the study and sign the informed consent.
- Except for the different doses of dexamethasone, participants will receive the routine medical care in OUMC.

3. Include the study duration and number of study visits required.

This study will last for 5 months. There is only one visit for patients who are in OUMC for more than 28 days after randomization. There are two visits for patients who are not in OUMC at day 28 after randomization, first visit is the same as prior mentioned first visit, the second visit is a phone visit. The first visit is for screening, informed consent. After the visit, participants will be randomized and receive dexamethasone 20mg daily vs. 6mg daily. Participants will receive other routine medical care in the hospital till discharge. Research staff will review the hospital medical records daily to monitor the clinical improvement and any adverse event. At day 28, if participants are not in OUMC, research team will contact participants to evaluate the WHO ordinal scale.

4. Describe blinding, including justification for blinding or not blinding the trial.

This is an open label trial. The study outcome is objective. Not blinding the trial does not affect the study outcome.

5. Include justification for inclusion of a placebo or non-treatment group.

This study does not include a placebo or non-treatment group. At least two

large clinical trials showed corticosteroids have benefit to COVID patients. Using placebo or non-treatment is not ethic.

6. Describe what happens to participants receiving therapy when study ends or if their participation in the study ends prematurely.  
 Participation of the study ends after day 28. The investigator will not contact the participants or give other interventions or suggestions after day 28.  
 Participants are welcome to contact the PI for any questions after study participation ends.

7. Indicate where the procedures will be completed.

- Include all sites where research activities will be conducted (consenting, interventions, chart reviews, data analysis, etc).  
 This research will be conducted in University of Oklahoma Health Sciences Center. Consenting and interventions will be conducted in University of Oklahoma Medical Center. Chart reviews and data analysis will be conducted in University of Oklahoma Medical Center and College of Medicine.
- Indicate that all required approvals are already obtained or will be obtained at each research location prior to project implementation.  
 This trial will be conducted at OUMC adult service. OUHSC IRB approval is needed. No other approval is needed. We will collaborate with other clinical services including emergency department and hospitalist service for participant recruitment. [name], study Co-PI and chief of pulmonary and critical care section will facilitate the collaborations.

8. Indicate whether clinically relevant research results, including individual research results, will be disclosed to participants. If so, under what conditions? The individual research results, including the oxygen support information, the length of hospital stay, ICU care, ventilator use etc, will communicate with participants/guardians during routine patient care. The final deidentified data analysis results may be published in literatures.

9. Identifiers might be removed and the de-identified information may be used for future research without additional informed consent from the subject.

